- H1 Metabolic phenotypes based on basic mechanisms of adipose tissue are associated to the cardiovascular risk modification after bariatric surgery.
- H0. Metabolic phenotypes based on basic mechanisms of adipose tissue are NOT associated to the cardiovascular risk modification after bariatric surgery.

GENERAL OBJETIVE

To evaluate the association of the cardiovascular benefit of the obese patient after bariatric surgery with the basic mechanisms of adipose tissue (metabolic profile)

SPECIFIC OBJECTIVES

- Characterize the basal (pre-surgical) metabolic profile of adipose tissue.
- Evaluate post-surgical modification of cardiovascular prognosis
- Determine the association of the cardiovascular prognosis modification (risk subgroups) with the basal metabolic profile.

DESIGN

This is an OBSERVATIONAL study, of a prospective cohort follow-up. We will study morbidly obese patients who undergo bariatric surgery (this is not a proposal of the present protocol, it is routinely done as a treatment for morbid obesity in the CMN "20 de Noviembre", ISSSTE, and it would also be carried out although the patient does not participate in this study). It was considered that the independent variable is the change in cardiovascular risk after bariatric surgery and the dependent variable is the basal metabolic profile of adipose tissue. This order of variables was decided by methodological strategy, since it will be more convenient to determine and stratify based on the change in cardiovascular risk, than based on the basal metabolic profile of adipose tissue.

$$n = \frac{(Z^{\alpha/2})^2 (p(1-p))}{d^2}$$

where:

n = sample size.

$Z^{\alpha/2} = Z$

value of the alpha error with a confidence of 95%, assigning alpha = 0.05

p =

Expected population prevalence for the event under study (according to previous reports).

d

=difference between the expected population prevalence value and the acceptable error. Considering the average difference in the modification of the basic mechanisms in adipose tissue associated with metabolic risk in similar studies

$$\begin{array}{ll}
 (1.96)^2 (0.20 (1-0.20)) & 0.614 \\
 n = \frac{\text{_____}}{(0.13)^2} & n = \frac{\text{_____}}{0.0169} = 36.3
 \end{array}$$

Additionally, for reasons of comparison and standardization of results, a C group would be considered: 10 non-obese patients undergoing non-bariatric surgery.

Definition of the observation units.

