Patients with morbid obesity subjected to bariatric surgery, with significant modification of cardiovascular risk in the postoperative period.

Definition of the control group

Due to the observational design of the before-after evaluation (of bariatric surgery), the morbidly obese patient in the pre-surgical baseline is his own reference ("control") for the postoperative period. It is also considered non-obese subjects subjected to abdominal surgery eg. Hernioplasty, fundoplication etc. to know the "normal" metabolic profile of adipose tissue.

Inclusion criteria

- Men and women.
- Over 18 years.
- With morbid obesity and candidates for bariatric surgery, under the routine of the treating service.
- Signature of acceptance of your participation, through informed consent.

Exclusion criteria.

- Medication with potential effect on fatty tissue or cardiovascular risk in the last month.
- Serious infections in the last month.
- Clinically unstable conditions.

Elimination criteria.

- Desire not to continue in the study
- Samples or insufficient information for an adequate analysis.

Definition of variables and units of measurement.

Definition of variables and units of measurement.			
Variable	Dependent / Independent	Type	Units of measurement
Total body fat, visceral and subcutaneous	Dependent	Discontinuous Quantitative	Percentage
Serum markers of inflammation PCR and IL-6	Dependent	Quantitative continuous	µUI / dL
Serum adipokines: leptin and adiponectin	Dependent	Quantitative continuous	µUI / dL
Differentiation and hypertrophy of adipocytes and angiogenesis	Dependent	Qualitative dichotomous	Present or absent
Pro-inflammatory markers at tissue level	Dependent	Qualitative dichotomous	Present or absent
Oxidative stress and tissue endoplasmic reticulum	Dependent	Qualitative dichotomous	Present or absent
Insulin sensitivity	Dependent	Qualitative dichotomous	Sensitive or not sensitive
HOMA	Dependent	Qualitative dichotomous	Higher or lower than 15
Prognostic scales mortality due to independent cardiovascular cause	Independent	Quantitative discontinuous	Own rating
Flow mediated dilatation	Independent	Quantitative discontinuous	Percentage
Carotid intima media thickness	Independent	Quantitative discontinuous	Millimeters

Selection of sources, methods, techniques and procedures for collecting information

With the acceptance of the Institutional Ethics, Research and Biosafety Committees, patients will be invited and included according to the selection criteria.

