Data analysis will be done through descriptive statistics applied to demographic variables, and inferential statistics, which will include difference of averages, correlation, strength of association and relative risk, as well as multivariate logistic regression analysis to evaluate independent associations. With the variables most associated with the modification of cardiovascular risk, a metabolic profile will be established as a predictive model of the greatest cardiovascular benefit after bariatric surgery. Statistical significance will be considered with $p < 0.05$

ETHICAL CONSIDERATIONS

This study is considered as minimal risk. Bariatric surgery (this procedure is not a proposal of the present protocol, it is routinely done as a treatment for morbid obesity in the CMN "20 de Noviembre", ISSSTE and would also be done if the patient does not participate in the study) will be performed according to the routine procedures of the Department of Bariatric Surgery. The project complies with the guidelines and recommendation of the Declaration of Helsinki. The protocol will be submitted to the Ethics and Institutional Research Committee. All patients will be asked to read and sign informed consent.

BIOSECURITY CONSIDERATIONS.

Bariatric surgery procedures are not part of this investigation. In any case, it is emphasized that this project does not alter the surgical procedure and routine biosecurity measures, which are based on the best clinical practice and international recommendations (Neff KJ, le Roux CW, Bariatric surgery: a best practice article. *Pathol* 2013; 66: 90-8). Sampling during surgery will be done in accordance with the Regulation of the General Health Law on Health Research, respecting aspects of taking the appropriate measures to avoid any risk or damage to research subjects (includes adequate preoperative assessment). , biosecurity measures typical of an operating room and sampling by an experienced surgeon). In any case, the privacy of the individual subject of the investigation will be protected, and it will be sought to limit the likelihood that the subject will suffer any harm as a result of the study.

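### The predictive model is selected and judged on the same roughly 37 patients at p < 0.05, with no primary measure, multiplicity rule or validation

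*Combined protocol and SAP*

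**What the plan says.** The combined protocol and SAP states a formal H1, that "Metabolic phenotypes based on basic mechanisms of adipose tissue are associated to the cardiovascular risk modification after bariatric surgery", with a matching H0. The third specific objective reads "Determine the association of the cardiovascular prognosis modification (risk subgroups) with the basal metabolic profile". The Design section makes the change in risk the grouping variable because "it will be more convenient to determine and stratify based on the change in cardiovascular risk", and the observation units are bariatric patients "with significant modification of cardiovascular risk in the postoperative period". Neither place gives a cut-off.

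The measures of risk differ between two lists:

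- The variables table has "Prognostic scales mortality due to independent cardiovascular cause", "Flow mediated dilatation" and carotid intima media thickness.
- The data-collection section has prognostic scales (Framingham or SCORE, left open), serum markers of endothelial dysfunction, ankle/arm index and carotid thickness. It sets follow-up at 3, 6 and 9 months.

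The processing plan lists mean differences, correlation, relative risk and multivariate logistic regression, and then says: "With the variables most associated with the modification of cardiovascular risk, a metabolic profile will be established as a predictive model". The model is meant to predict the greatest cardiovascular benefit, and significance is p < 0.05. No section names a primary measure or visit, defines that benefit, says how markers are chosen, adjusts for multiplicity, or provides a data split, cross-validation, bootstrap or second bariatric cohort.

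**The concern.** Choosing the markers that look best in a small sample and then assessing them in that same sample uses the data twice. The p-value of the resulting model no longer has its nominal meaning, and its discrimination is overstated even when every marker is noise.

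The rule for selection is also undefined. It could mean the top-ranked markers, or only those with p < 0.05. A plain comparison of baseline markers across risk subgroups, which the Design section outlines, does not escape the problem, because nothing says which marker, measure, visit or cut-off decides H1, or whether one significant marker is enough.

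H1 and the predictive model are what the study sets out to deliver. As written, a chance profile could be reported as confirming H1, with an AUC that looks good.

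**Working it through.** **Sample size.** Inputs from the Design section are z = 1.96, d = 0.13 and p = 0.20, described as "Expected population prevalence for the event under study". Then n = 1.96² × 0.20 × 0.80 / 0.13² = 0.6147 / 0.0169 = 36.4. This reproduces the stated 36.3 and rounds up to 37. The formula gives the precision of one proportion; it does not size a test of H1 or a prediction model. The 10 non-obese patients do not have bariatric surgery, so they cannot validate a model of benefit after it.

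**Events.** The plan does not say that p = 0.20 is the rate of cardiovascular benefit. If it were, 0.20 × 37 = 7.4, or about 7 events against 30 non-events. A three-marker logistic model would then have 7/3 ≈ 2.3 events per marker. A near-even split, 18 against 19, was also examined.

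**Candidate markers**, under three counts:

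- 8: the dependent-variable rows of the variables table.
- 15: the single items in those rows.
- 27: CT fat 5 + tissue features 7 × 2 depots = 14 + serum 6 = 25, plus insulin sensitivity and HOMA. Liver items are left out because liver is sampled only in some patients.

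**Risk outcomes.** The two lists together give 5 measures. At 3 visits that is 5 × 3 = 15 outcomes.

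**Independent markers, one outcome.** The chance of at least one false positive is 1 − 0.95^m: 34% for m = 8, 54% for m = 15 and 75% for m = 27.

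**Correlated markers.** These are null simulations with n = 37, equicorrelated normal markers, one measure at one visit and 4,000 runs per cell. Each range runs from inter-marker correlation 0.7 down to 0. Logistic rows use 7 events and a likelihood ratio test; the linear row uses an F test.

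| Result at p < 0.05 with no true association | 8 markers | 15 markers | 27 markers |
|---|---|---|---|
| At least one marker, 7 v 30 | 20–33% | 27–53% | 34–77% |
| Logistic model, only markers with p < 0.05 enter (at most 3) | 17–33% | 21–53% | 26–76% |
| Logistic model, best 3 enter regardless | 14–35% | 20–63% | 25–87% |
| Linear model, continuous outcome, best 3 | 10–26% | 14–54% | 20–80% |

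For reference, three markers fixed in advance give about 8% (logistic) and 5% (linear). A small part of the logistic figures is therefore small-sample error, not selection.

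**Apparent AUC, best 3 markers.** The mean is 0.72–0.87 with 7 events and 0.68–0.80 with 18, against a true 0.50. With 18 events the any-marker rates are 19–34%, 25–54% and 33–77%, so the result does not depend on the assumed 20%.

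**Several outcomes.** If 3 measures at 3 visits were all searched, at least one marker would be significant in 74% to over 99% of runs. This assumes correlation 0.7 between visits, 0.3 between measures and 0.3–0.7 between markers. The plan does not say that all are searched, so the conclusion does not rest on this figure.

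**The case against.** The strongest reply is that this is biomarker discovery. The title speaks of potential utility, the Justification says that the study explores, surgery is routine care, and no treatment decision depends on the model. Labelling the model exploratory and correcting its performance would remove much of the harm. That is fair, and it is part of the fix. But the plan states a formal H1/H0, promises a predictive model and does not itself label the model exploratory.

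Other objections, and what stands of them:

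- **A third reading of the selection.** The chosen variables may be those retained in the multivariate logistic regression. Approximated by forward entry at p < 0.05, this gives a significant result in 23–81% of null runs, so it is no safer.
- **Marker type.** The table used normal markers, whereas the variables table makes 5 of 8 rows (8 of 15 items) dichotomous. Using Fisher's exact test for those items trims the upper any-marker figures to about 29% and 48%. The direction is unchanged.
- **Linear figures.** The processing plan names logistic but not linear regression. It does name correlation, and the logistic rows stand alone.
- **An implied lead measure.** The objectives speak of prognosis, which may point to the prognostic scales. The data-collection section nevertheless treats all its items as measures of risk modification and leaves Framingham or SCORE open.
- **Inferred inputs.** The use of the same patients is inferred from there being one bariatric cohort and no split. The number analysed and the event count are also assumptions, and exclusions for insufficient samples could reduce the cohort further.

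**Conclusion.** The concern holds. Following the plan as written gives an error rate above the nominal 5% for H1 and an optimistic model. With one measure at one visit, the smallest logistic or any-marker figure is 14% (8 markers, correlation 0.7, best three entered) and the largest is 87% (27 independent markers). Apparent AUC averages 0.72–0.87 with 7 events, or 0.68–0.80 with 18, where the truth is 0.50.

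The exact size rests on the assumed marker counts, correlations, event numbers and 37 analysed patients. The direction does not: every combination examined exceeds 5%, whether markers enter by rank, by p-value or by forward selection, and also when they are only compared between subgroups. This should be corrected before analysis.

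**What to change.** In the processing plan:

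1. **Outcome.** Name one primary risk measure and one visit, and the scale if a score is used. Analyse its change as a continuous variable, and state in advance the cut-off for any subgroup or logistic analysis. Reconcile the two lists of measures. Make the remaining measures and visits secondary, either multiplicity-controlled or labelled exploratory.
2. **Test of H1.** Test it once. Use either a profile defined without the outcome (two or three markers listed beforehand, or the first principal component of the baseline markers) or a permutation test that repeats the whole selection. In null runs, type I error was 3.4–6.1% for the principal component. For the permutation test it was 3.4–4.6% (linear) and 5.1–5.5% (logistic, 1,000 runs; 4.8–7.8% in smaller 400-run cells).
3. **Model.** If the outcome-driven profile is kept, repeat the selection inside every fold of repeated stratified cross-validation, report that AUC with an interval, and label the model exploratory and not validated. In null runs the mean AUC was 0.48–0.51. Bootstrap correction with the selection repeated still left 0.59–0.67 with 7 events, so it is not sufficient here.

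The cost is plan wording and modest programming, with no new patients or measurements. There will be fewer nominally significant results, and power is limited. For a true correlation of 0.5, a continuous outcome and marker correlations of 0.3–0.7:

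| Test of H1 | Power, signal shared by all markers | Power, one marker carries it |
|---|---|---|
| First principal component | 78–90% | 39–76% |
| Permutation repeating the selection | 51–72% | 43–61% |
| Three pre-listed markers | 45–71% | 74–80% if the right one is listed |

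Splitting patients 7 v 30 lowers the principal-component power for a shared signal to 44–57%, which is the reason to prefer a continuous outcome even though the Design section chose to stratify. The cross-validated AUC is close to unbiased but imprecise: its SD is 0.16–0.18 with 7 events.
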